11.3 Demographic and Baseline Characteristics

Demographic characteristics will be summarized by treatment group. The following demographic characteristics will be summarized for all data sets:

1. Continuous baseline variables: age (years)
2. Categorical baseline variables:
 - Age (< 65, ≥ 65 years)
 - Gender (female, male)
 - Ethnicity (Hispanic, not Hispanic); and
 - Race (American Indian or Alaska Native, Asian, Black or African American, Native Hawaiian or Other Pacific Islander, White, Other)

Summary statistics (sample size, mean, median, standard deviation (SD), minimum and maximum for continuous variables and sample size, counts and percentages for categorical variables) will be provided by treatment group. A listing of randomized treatment assignment for each subject, their evaluability status and demographic characteristics will be provided.

Visit 1 (Baseline/Day 0) summary statistics will be presented overall and by treatment group. Descriptive statistics (sample size, mean, SD, minimum and maximum) will be presented by treatment at Visit 1 for TFBUT, LLT AUC₁₂₀, Global Ocular Discomfort VAS score, [REDACTED]

[REDACTED] BCVA, and slit-lamp examination.

11.4 Efficacy Analyses

The study eye will be the worst eye at baseline for each parameter. If the baseline values are equivalent, the right eye will be selected.

11.4.1 Primary Efficacy

The primary objective of this study is to demonstrate noninferiority of SYSTANE BALANCE over RERESH OPTIVE ADVANCED using TFBUT after 35 days of QID dosing in subjects with lipid-deficient dry eye.

The primary endpoint is the change from baseline at Day 35 in TFBUT. The TFBUT will be assessed at Visit 1 (Day 0), Visit 2 (Day 15), and Visit 3 (Day 35).

11.4.1.1 Statistical Hypotheses

The primary efficacy hypothesis is that SYSTANE BALANCE is noninferior to REFRESH OPTIVE ADVANCED with respect to the change from baseline in TFBUT at Day 35 in subjects with lipid-deficient dry eye.

The null and alternative hypotheses are:

$$H_0: \mu_{SB} - \mu_{OA} \leq -1$$

$$H_1: \mu_{SB} - \mu_{OA} > -1$$

where μ_{SB} and μ_{OA} denote the mean change from baseline in TFBUT at Day 35 for SYSTANE BALANCE and REFRESH OPTIVE ADVANCED, respectively.

The noninferiority margin was chosen as 1 second on the basis that an increase of at least 25% in the baseline TFBUT of a patient with lipid-deficient dry eye would be considered clinically meaningful since the patient would blink less often. Based on historical data, the mean TFBUT at baseline for a patient with lipid-deficient dry eye is approximately 4 seconds.

11.4.1.2 Analysis Methods

The primary efficacy analysis population will be the PPS.

The analysis of the primary efficacy parameter, change from baseline in TFBUT at Day 35 in the study eye, will be based on a mixed model repeated measures (MMRM) analysis. The mixed model will include terms for baseline TFBUT, treatment (SYSTANE BALANCE,

REFRESH OPTIVE Advanced), visit (Day 15, Day 35), and treatment-by-visit interaction. The response variable is the change from baseline in TFBUT for the study eye.

An unstructured variance-covariance matrix will be used to model the within-subject correlation. If the unstructured variance-covariance matrix results in a lack of convergence then other covariance structures will be investigated.

Within-treatment and estimates of the difference (SYSTANE BALANCE – REFRESH OPTIVE Advanced) in mean change from baseline in TFBUT between SYSTANE BALANCE and REFRESH OPTIVE Advanced and associated 95% CI will be presented. Evidence of noninferiority will be deemed established if the lower limit of the 95% CI for the difference is above -1.0.

11.4.2 Secondary Efficacy

The secondary efficacy objectives are:

- To demonstrate that SYSTANE BALANCE is superior to REFRESH OPTIVE Advanced using TFBUT after 35 days of QID dosing in subjects with lipid-deficient dry eye.
- To evaluate changes in LLT AUC₁₂₀ following the use of SYSTANE BALANCE versus REFRESH OPTIVE Advanced after 35 days of QID dosing in subjects with lipid-deficient dry eye.
- To evaluate changes in Global Ocular Discomfort using a VAS score following use of SYSTANE BALANCE versus REFRESH OPTIVE Advanced after 35 days of QID dosing in subjects with lipid-deficient dry eye.

The secondary efficacy endpoints are:

- Change from baseline in TFBUT at Day 35
- LLT AUC₁₂₀ at Day 35
- Change from baseline in Global Ocular Discomfort VAS score at Day 35

11.4.2.1 Statistical Hypotheses

The hypotheses for the secondary analysis are:

- SYSTANE BALANCE is superior to REFRESH OPTIVE Advanced with respect to change from baseline in TFBUT at Day 35
- SYSTANE BALANCE is superior to REFRESH OPTIVE Advanced with respect to LLT AUC₁₂₀ at Day 35

- SYSTANE BALANCE is superior to REFRESH OPTIVE Advanced with respect to change from baseline in Global Ocular Discomfort VAS score at Day 35

The null and alternative hypotheses for the first secondary endpoint are:

$$H_0: \mu_{SB} - \mu_{OA} \leq 0$$

$H_1: \mu_{SB} - \mu_{OA} > 0$ where μ_{SB} and μ_{OA} denote the mean change from baseline in TFBUT at Day 35 for SYSTANE BALANCE and REFRESH OPTIVE Advanced, respectively.

The null and alternative hypotheses for the second secondary endpoint are:

$$H_0: \mu_{SB} - \mu_{OA} \leq 0$$

$$H_1: \mu_{SB} - \mu_{OA} > 0$$

where μ_{SB} and μ_{OA} denote the mean LLT AUC₁₂₀ at Day 35 for SYSTANE BALANCE and REFRESH OPTIVE Advanced, respectively.

The null and alternative hypotheses for the third secondary endpoint are:

$$H_0: \mu_{SB} - \mu_{OA} \geq 0$$

[figure not shown]
$$H_1: \mu_{SB} - \mu_{OA} < 0$$

where μ_{SB} and μ_{OA} denote the mean change from baseline in VAS score at Day 35 for SYSTANE BALANCE and REFRESH OPTIVE Advanced, respectively.

11.4.2.2 Analysis Methods

The analysis of the secondary efficacy parameter LLT AUC₁₂₀ at Day 35, and change from baseline in Global Ocular Discomfort VAS score at Day 35, and change from baseline of the TFBUT at Day 35 will be based on a MMRM. The mixed model will include terms for baseline parameter values, treatment, visit (Day 15, Day 35), and treatment-by-visit interaction. Estimates of the difference in mean change from baseline between SYSTANE BALANCE and REFRESH OPTIVE Advanced and associated 95% CIs will be presented.

Each endpoint will be evaluated for superiority of SYSTANE BALANCE over REFRESH OPTIVE Advanced. The p-value from the one-sided test less than 0.025 for a difference in favor of SYSTANE BALANCE will indicate superiority of SYSTANE BALANCE over REFRESH OPTIVE Advanced.

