11.6 Multiplicity

To ensure overall control of the type I error rate, the secondary efficacy hypotheses will be relevant only if the primary efficacy null hypothesis is first rejected at the 5% level of significance (2-sided). Following the rejection of the primary efficacy null hypothesis, the secondary hypotheses will be tested following the Hochberg testing procedure.

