Unless otherwise specified, all statistical tests will be two-sided and performed using a 5% significance level, leading to 95% (two-sided) confidence intervals (CIs). If a CI is presented for the proportion of a categorical variable, then the exact Clopper-Pearson method will be used to calculate the 2-sided 95% CI.

All data will be listed by subject and eye, unless stated otherwise.

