5.3.1 Multiplicity Strategy

To ensure overall control of the type I error rate, following the rejection of the primary efficacy null hypothesis (if the lower limit of the 95% CI [equivalent to the 1-sided 97.5% CI] for the difference of the primary efficacy endpoint is above -1.0 second), the secondary hypotheses will be tested using the Hochberg testing procedure.

For the secondary efficacy endpoints, let:

- H_{0i} refers to the corresponding null hypotheses
- p_i refers to the p-values for H_{0i} , which will be calculated without any multiplicity adjustment where $i = 1, \dots, k$ such that $[1], \dots, [k]$ refer to the order from $p_{[1]} \leq \dots \leq p_{[k]}$.
- Hochberg’s step-up method will proceed as follows:
 - Step 1: If $p_{[k]} < \alpha$ (where α is 0.025, 1-sided), reject all H_{0i} (where $i = 1, \dots, k$), and stop; otherwise go to Step 2.
 - Step 2: If $p_{[k-1]} < \alpha/2$ (where α is 0.025, 1-sided), reject $H_{0[i]}$, $i = 1, \dots, k - 1$, and stop; otherwise go to Step 3.

- ...
- Step k: If $p_{[i]} < \alpha/k$ (where α is 0.025, 1-sided), reject $H_{0[i]}$, $i = 1$, and stop.

Both the adjusted and unadjusted p-values for the secondary efficacy endpoints will be presented.

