12.1 SAS code

12.1.1 Mixed model repeated measures

This SAS code will be used for the MMRM analysis for the primary and relevant secondary endpoints.

```
proc mixed data=<analysis dataset>;  
class usubjid treatment visit;  
model <endpoint of interest>=<baseline of endpoint of interest> treatment  
visit treatment*visit/solution ddfm=kr;  
repeated visit / subject=usubjid type=un;  
lsmeans treatment*visit / pdiff=all cl alpha=0.05 slice=visit;  
run;
```

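### Protocol 11.4.2.2 gives a flat one-sided 0.025 superiority rule that is not reconciled with Hochberg, and the SAP states no one-sided conversion of the p-values and reverses the VAS alternative

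*Protocol*

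**What the plan says.** **Decision rule.** Protocol 11.4.2.2, covering every secondary endpoint, ends with: "The p-value from the one-sided test less than 0.025 for a difference in favor of SYSTANE BALANCE will indicate superiority". It neither mentions nor points to section 11.6. Protocol 11.6 requires the primary null to be rejected first, and then "the secondary hypotheses will be tested following the Hochberg testing procedure". The protocol synopsis agrees with 11.6. SAP 5.3.1 repeats that "the secondary hypotheses will be tested using the Hochberg testing procedure" and writes out the steps with alpha 0.025, one-sided: 0.025 for the largest p-value, then alpha/2, and so on. The current SAP keeps two secondary hypotheses, TFBUT and VAS. LLT is only listed (SAP 11.1).

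**P-values.** SAP 5.3.1 describes the p-values for the secondary nulls as ones "which will be calculated without any multiplicity adjustment" and promises that "Both the adjusted and unadjusted p-values for the secondary efficacy endpoints will be presented". It does not say how a one-sided p-value is obtained. SAP section 2 sets the default: "Unless otherwise specified, all statistical tests will be two-sided and performed using a 5% significance level". The code in SAP 12.1.1, given for the primary and relevant secondary endpoints, uses "lsmeans treatment*visit / pdiff=all cl alpha=0.05 slice=visit".

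**Direction for VAS.** Protocol 11.4.2.1 has H0: difference ≥ 0 and H1: difference < 0. SAP 5.2 has H0: difference ≤ 0 and H1: difference > 0. Both define the difference as SYSTANE BALANCE minus comparator in mean change from baseline.

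**The concern.** Superiority on TFBUT and on VAS are the only confirmatory claims left beyond noninferiority. The same pair of p-values should lead to one conclusion whichever section is cited. Here it may not. A TFBUT p of 0.020 with a VAS p of 0.30 is superior on TFBUT under 11.4.2.2 and not superior under Hochberg.

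The inputs to Hochberg are also open to two slips. An analyst could compare the printed two-sided p-values with one-sided thresholds. Or an analyst could convert them using the SAP's own VAS hypothesis, which looks in the tail opposite to the protocol's. Because the VAS p-value also decides which threshold TFBUT faces, an error there can change both claims.

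**Working it through.** **1. The plan's own figure.** Inputs from Protocol 11.10 and SAP 9: SD 2.5, margin 1.0 s, true difference 0, one-sided 0.025, 80% power. Normal approximation: n per arm = 2 × 2.5² × (1.960 + 0.842)² / 1.0² = 98.1, so 99 per arm and 198 in total. The noncentral t gives 200, as stated, and all six rows of the sample size table reproduce. Power at 100 per arm is 0.804 (t) or 0.807 (normal). This is not in dispute; it supplies the gate in step 4.

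**2. Where the rules differ (two endpoints).**
- Both one-sided p < 0.025: both rules reject both nulls.
- Smaller p < 0.0125, larger ≥ 0.025: both rules reject only the endpoint with the smaller p.
- Smaller p from 0.0125 to below 0.025, larger ≥ 0.025: the flat rule rejects one null, Hochberg none.
- Both ≥ 0.025: neither rule rejects.

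Only the third case is in conflict.

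**3. Family-wise one-sided error, both nulls true, before the noninferiority gate.**
- Flat rule, independent endpoints: 1 − 0.975² = 0.0494.
- Hochberg, independent endpoints: 0.025² + 2 × 0.0125 × 0.975 = 0.000625 + 0.024375 = 0.0250.

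The documents give no correlation between the endpoints, so other values are assumed (bivariate normal, 2 million draws):

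| Correlation | Flat rule | Hochberg |
|---|---|---|
| 0 | 0.0494 | 0.0250 |
| 0.3 | 0.0476 | 0.0246 |
| 0.5 | 0.0453 | 0.0240 |

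**4. With the noninferiority gate at the design assumptions.** Standard error = 2.5 × √(2/100) = 0.354. The gate is passed when Z for TFBUT exceeds 1.960 − 1/0.354 = −0.868, with probability 0.807. For independent endpoints:
- Flat rule: 0.025 + 0.025 × (0.807 − 0.025) = 0.0446 (simulation 0.0447).
- Hochberg: 0.0006 + 0.0125 × 0.975 + 0.0125 × (0.807 − 0.025) = 0.0226 (simulation 0.0225).

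This simplifies to one analysis set; the plan uses the PPS for the gate and the FAS for superiority.

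**5. Two-sided p-values used unconverted.** A two-sided p compared with 0.025 and 0.0125 is, for a favourable result, a one-sided test at 0.0125 and 0.00625. The simulated favourable-direction family-wise error is 0.0125 (independent), half the intended level, so the slip is conservative for claims. The cost is power. A single test with 80% power at one-sided 0.025 has 71% at 0.0125 and 62% at 0.00625 (normal approximation). These are single-test values, not power of the Hochberg procedure, and the 80% is a premise: the documents state no power for superiority.

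**6. The VAS tail.** The one-sided p is p/2 when the estimate lies in the direction of H1, and 1 − p/2 otherwise. Suppose VAS has a two-sided p of 0.010 with the estimate below 0, and TFBUT has a one-sided p of 0.020.
- Protocol direction: VAS p = 0.005. The larger p is 0.020, below 0.025, so both nulls are rejected.
- SAP 5.2 taken literally: VAS p = 1 − 0.005 = 0.995. The larger p fails at 0.025, and the smaller, 0.020, fails at 0.0125. Neither null is rejected.

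With the VAS estimate above 0 and the same two-sided p, the SAP wording would give 0.005 and count as VAS superiority a result that the protocol treats as unfavourable.

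**The case against.** The best defence is that the plan has one decision rule. Protocol 11.4.2.2 gives the level and direction of each test; 11.6 and the synopsis say how the secondary hypotheses are decided. The value 0.025 is also Hochberg's first-step threshold and the cut-off for a Hochberg-adjusted p-value. SAP 5.3.1 gives the whole algorithm, and the SAP does not repeat the flat rule. As Hochberg is already in the protocol, SAP 11.1 had nothing to list on that account. Most of this stands. A reader might infer that the trial lacks multiplicity control or runs at nearly twice its stated error rate; the documents do not support that, because the 4.9% belongs to a procedure that the SAP does not adopt. The three-endpoint figure, 1 − 0.975³ = 7.3%, does not apply to the current SAP either.

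On sidedness, the nulls in SAP 5.2 are one-sided and alpha is labelled one-sided at each step, which overrides the two-sided default. A reader might also infer that the SAP contains only code that yields the wrong p-values. That cannot be verified: the SAP contents show a redacted entry after 12.1.1. The visible code is a model template that computes no adjusted p-values, so further programming must exist. Nor would unsigned p-values by themselves license a claim for a result favouring the comparator, since 11.4.2.2 requires a difference in favour of SYSTANE BALANCE.

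What the defence does not answer is that the 11.4.2.2 sentence is unqualified, that no conversion is written down, and that the two documents give opposite VAS alternatives. The last point weakens the appeal to the written hypotheses as settling direction.

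**Conclusion.** The point holds as a reconciliation of decision rules. Protocol 11.4.2.2, read literally, differs from Hochberg in one band: smaller one-sided p from 0.0125 to below 0.025, with the larger at least 0.025. If the flat rule were used alone, family-wise one-sided error would be about 4.9% for independent endpoints, 4.5% at an assumed correlation of 0.5, and about 4.5% for independent endpoints with the gate at the design assumptions, against 2.5% or less with Hochberg. Hochberg is plainly intended, so the risk is a borderline result being read two ways.

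The missing one-sided conversion is a specification gap. Used unconverted, the printed p-values lose power and do not inflate favourable claims. The reversed VAS alternative in SAP 5.2 is the sharper problem: taken literally, it tests the wrong tail for VAS and, through Hochberg, can alter the TFBUT conclusion too. The primary noninferiority decision uses the 95% CI and is untouched.

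**What to change.** 1. Protocol 11.4.2.2: make the superiority sentence subject to the Hochberg procedure in 11.6, or record this clarification in SAP 11.1.
2. SAP 5.3.1: define each p-value as the one-sided p-value of the Day 35 contrast, SYSTANE BALANCE minus comparator, in the tail favouring SYSTANE BALANCE (upper for TFBUT, lower for VAS). State that the adjusted and unadjusted p-values reported are one-sided.
3. SAP 5.2: correct the VAS hypotheses to H0: difference ≥ 0 and H1: difference < 0, matching Protocol 11.4.2.1.
4. SAP 12.1.1: add the signed Day 35 contrast with its one-sided p-value (for example an `LSMESTIMATE` statement, upper-tailed for TFBUT and lower-tailed for VAS), and keep the two-sided 95% CI.

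The cost is a few sentences and one line of code, with no new data. SAP 11.1 says that at Version 3.0 the database was not yet locked and the treatment code was unbroken, so the change could be made while masked.

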11.5 Handling of Missing Data

The mixed-effects repeated measures (MMRM) model approach will be used to analyze the continuous variables. The MMRM model is suitable for longitudinal data with missing values

under the missing at random (MAR) assumption. It is a likelihood-based analysis that can provide valid inference without the need for explicit modeling or imputation of missing data.

11.6 Multiplicity

To ensure overall control of the type I error rate, the secondary efficacy hypotheses will be relevant only if the primary efficacy null hypothesis is first rejected at the 5% level of significance (2-sided). Following the rejection of the primary efficacy null hypothesis, the secondary hypotheses will be tested following the Hochberg testing procedure.

11.7 Safety Analysis

The safety endpoints in this study are:

- AEs
- BCVA
- Slit-lamp examination (cornea, lens, iris and anterior chamber)

The safety analyses will consist of summaries of the AEs and measured safety parameter data. This will include summaries of BCVA and slit-lamp in addition to AEs. The statistics presented for each endpoint will be relevant to the measure of the value, ie, whether the data are categorical or numeric. Continuous measurements will be presented using number, mean, standard deviation, minimum and maximum at each visit. Categorical measurements will be tabulated with the number and percent of subjects in each category at each visit. No inferential testing will be performed for the safety analyses.

11.8 Health Economics

Not applicable.

11.9 Interim Analyses

Not applicable.

11.10 Sample Size Justification

In this study, approximately 220 subjects will be randomized to SYSTANE BALANCE or REFRESH OPTIVE Advanced in a 1:1 ratio in order to achieve 200 evaluable subjects. A total of 200 subjects provides approximately 80% power to reject the null hypothesis of

inferiority of mean change from baseline in TFBUT at the 0.025 level of significance (1-sided), assuming a treatment difference of 0.0, a standard deviation of 2.5, and a noninferiority margin of 1.0 second.

Table 11–1 shows the sample size required to achieve 80% and 90% power with different assumed values of standard deviation.

Table 11–1 Sample Size Calculation

Power	Assumed standard deviation	Sample size (total evaluable)
80%	2.5	200
	2.75	240
	3.0	286
90%	2.5	266
	2.75	320
	3.0	382

12 COLLECTION OF COMPLAINTS

12.1 General Information

Adverse Event

An AE is any untoward medical occurrence in a subject who is administered a study product regardless of whether or not the event has a causal relationship with the treatment. An AE, therefore, can be any unfavorable or unintended sign (including an abnormal laboratory finding), symptom, or disease temporally associated with the study product, whether or not related to the treatment. In clinical studies, an AE can include an untoward medical occurrence occurring at any time, including run-in or washout periods, even if no study product has been administered. The determination of clinical relevance is based upon the medical judgment of the Investigator.

Quality Complaints

Deficiency of a product includes inadequacy with respect to its identity, quality, durability, reliability, safety or performance. Note: This definition includes malfunctions, use errors, and inadequate labeling.

- Malfunction is defined as a failure of a product to meet its performance specifications or otherwise perform as intended. Performance specifications include all claims made in the labeling of the product. The intended performance of the product refers to the intended use for which it is labeled or marketed.

Use error is defined as the act or omission of an act that results in a different medical device response than intended by manufacturer or expected by user.

Adverse Drug/Device Effect (ADE)

An ADE is defined as an AE related to the use of study product. *Note: This definition includes AEs resulting from insufficient or inadequate instructions for use, deployment, implantation, installation, or operation; any malfunction; and use error or intentional misuse of the study product.*

Serious Adverse Event (SAE)

Adverse event that led to any of the following:

- Death
- A serious deterioration in health that either resulted in:
 - a. A life-threatening illness or injury.

Note: Life-threatening means that the individual was at immediate risk of death from the event as it occurred, ie, it does not include an event which hypothetically might have caused death had it occurred in a more severe form.

- b. Any potentially sight-threatening event or permanent impairment to a body structure or a body function.
- c. In-patient hospitalization or prolonged hospitalization

Note: Planned hospitalization for a pre-existing condition, or a procedure required by the clinical investigation plan, without serious deterioration in health, is not considered a SAE. In general, hospitalization signifies that the individual remained at the hospital or emergency ward for observation and/or treatment (usually involving an overnight stay) that would not have been appropriate in the physician's office or an out-patient setting. Complications that occur during hospitalization are AEs. If a complication prolongs hospitalization

or fulfills any other serious criteria, the event is serious. When in doubt as to whether "hospitalization" occurred, the event should be considered serious.

- d. A medical intervention to prevent a) or b), or any surgical intervention.
 - e. Any indirect harm as a consequence of incorrect diagnostic test results when used within manufacturer's instructions for use.
- Fetal distress, fetal death, or a congenital abnormality or birth defect.

Note: This includes quality complaints that might have led to a SAE if:

- a. suitable action had not been taken or
 - b. intervention had not been made or
 - c. circumstances had been less fortunate. These are handled under the SAE reporting system.
- Is an important medical event. An important medical event is an event that may not result in death, be life-threatening, or require hospitalization but may be considered an SAE when, based upon appropriate medical judgment, it may jeopardize the subject and may require medical or surgical intervention to prevent one of the outcomes listed in the definitions for SAEs. Examples of such medical events include allergic bronchospasm requiring intensive treatment in an emergency room or at home, blood dyscrasias or convulsions that do not result in a subject's hospitalization, or the development of drug dependency or drug abuse.

Serious Public Health Threat

Any event type which results in imminent risk of death, serious deterioration in state of health, or serious illness that requires prompt remedial action. This would include events that are of significant and unexpected nature such that they become alarming as a potential public health hazard, eg, human immunodeficiency virus (HIV) or Creutzfeldt-Jacob Disease (CJD).

Nonserious adverse event

Any AE that does not meet seriousness criteria described above.

Contributory cause (causality assessment)

In assessing the association of the device/product to the event, the following should be taken into account:

- The opinion, based on available evidence, of healthcare professionals
- The results of the preliminary assessment of the event
- Evidence of previous, similar events

This judgment may be difficult when there are multiple devices/products and drugs involved. In complex situations, it should be assumed that the device may have caused or contributed to the event and the MANUFACTURERS should err on the side of caution.

Reference Safety Information

For SAEs potentially qualifying expedited reporting, the following will serve as the reference safety information for the purposes of determining expectedness:

- Product Label for SYSTANE BALANCE

